2.2 TRIAL OBJECTIVES

The primary objective of this trial is to establish equivalence in efficacy between BI 695501 and US-licensed Humira at Week 16 in patients with active moderate to severe chronic plaque psoriasis.

The secondary objectives of this trial are to compare the safety and efficacy profiles of BI 695501 and US-licensed Humira.

A description of the selected endpoints and the observations along with specific information on how to collect the data is provided in [Section 5](#).

2.3 BENEFIT-RISK ASSESSMENT

Participation in this study may help to generate future benefit for larger groups of patients with psoriasis.

Patient risk will be minimized in this trial by implementing conservative eligibility criteria. Adverse events, body temperature, vital signs, electrocardiograms (ECGs) and safety laboratories as well as immunogenicity will be monitored at different time points during the trial and during the long term safety follow-up period up to 10 weeks after the last administration of trial medication.

Although rare, a potential for drug-induced liver injury (DILI) is under constant surveillance by sponsors and regulators. Therefore, this trial requires timely detection, evaluation, and follow-up of laboratory alterations in selected liver laboratory parameters to ensure patients' safety, see also Section [5.3.6.1](#).

All safety aspects will be regularly monitored by both the Sponsor and a Contract Research Organization (CRO) during the Medical Quality Review Meetings.

To avoid a risk of reactivating TB and other infections, TB tests (interferon-gamma release assay [IGRA] or purified protein derivative [PPD] skin test), Hepatitis B surface antigen (HBsAg; qualitative), Hepatitis B antibody (anti-HBc; qualitative), Hepatitis C antibodies (Anti-HCV; qualitative), human immunodeficiency virus (HIV)-1 and HIV-2 antibody (at the discretion of the investigator where clinically indicated) will be performed to exclude subjects who test positive. Risk to subjects will also be minimized in this trial by implementing conservative eligibility criteria.

In the controlled portions of clinical trials of some TNF-inhibitors, including Humira, more cases of malignancies have been observed among TNF-inhibitor-treated adult patients compared to control-treated adult patients. Therefore, a possibly increased risk for the development of malignancies cannot be excluded.

TNF-antagonists including Humira have been associated, in rare instances, with new onset or exacerbation of clinical symptoms and / or radiographic evidence of central nervous system demyelinating disease, including multiple sclerosis and optic neuritis, and peripheral demyelinating disease including Guillain-Barre syndrome. Prescribers should exercise caution in considering the use of Humira in patients with pre-existing or recent-onset central or peripheral nervous system demyelinating disorders.

To minimize the risks, patients with a significant disease other than psoriasis will be excluded from the trial participation.

The PK similarity of BI 695501 to US-licensed and EU-approved Humira was established in the phase I trial 1297.8 ([c03070713](#)). Additionally, there were no notable differences with respect to safety, tolerability, and immunogenicity between BI 695501 to US-licensed and EU-approved Humira in this phase I trial, and the dose of 40 mg BI 695501 was safe and well tolerated in male healthy volunteers. The observed blinded AE profile in the phase III trial 1297.2 ([c02158186](#)) revealed no unexpected safety findings and showed no clinically relevant safety concerns. The review of safety data in 1297.2 trial by the Independent Data Monitoring Committee (IDMC) to date has not suggested any clinically relevant differences in safety profile between Humira and BI 695501.

There were no clinically relevant findings with respect to clinical laboratory evaluation, vital signs, ECGs, or injection site reactions. Based on extensive preclinical, analytical, functional, and toxicological testing carried out prior to initiation of this trial, and the Phase I data described above, BI 695501, as a proposed biosimilar to Humira, is expected to show a similar efficacy, safety, immunogenicity and PK profile in patients with psoriasis.

Patients not achieving at least PASI 50 (patients showing lack of efficacy), will not continue receiving their treatment up to Week 24 with the study drug, but only followed up for safety. These patients will receive an alternative treatment as deemed appropriate by the investigator.

The benefit-risk profile for the patients participating in this trial remains favorable and similar to the originator product.

3. DESCRIPTION OF DESIGN AND TRIAL POPULATION

3.1 OVERALL TRIAL DESIGN AND PLAN

This is a multinational, randomized, double-blind, parallel-arm, multiple-dose, active comparator trial of BI 695501 and US-licensed Humira.

In total, approximately 300 patients with moderate to severe chronic plaque psoriasis are planned to be randomized in this trial.

Patients are included in the study once they have signed the informed consent. Patients suitable after screening will be eligible to participate in the 24-week treatment period and will be randomized at a ratio of 1:1 in a blinded fashion to 1 of 2 treatment arms (BI 695501 or US-licensed Humira) shown in [Figure 3.1: 1](#).

After Week 16, only patients who achieve at least a 50% reduction in Psoriasis Area and Severity Index (PASI 50) response will continue the trial receiving their randomized treatment up to Week 24. Those patients not achieving at least PASI 50 (or who discontinue the trial early), will not be treated with the study drugs, but only followed up for safety. Patients will undergo visits and trial procedures as shown in the [Flow Chart](#).

All patients who receive at least 1 injection of BI 695501 will have a Safety Follow-up visit 10 weeks after the last dose of trial medication.

Every effort should be made for all patients who complete the 24-week treatment period or who discontinue the trial early (and do not withdraw their consent), to return for a safety follow-up visit 10 weeks after the last administration of trial medication.

[figure not shown]

Figure 3.1: 1 Trial design

3.1.1 Administrative structure of the trial

The trial is sponsored by Boehringer Ingelheim International (BI).

CRO will perform Project Management, Clinical Field Monitoring, Medical Monitoring, Data Management, and Statistical Evaluation according to CRO Standard Operating Procedures (SOPs). A list of responsible persons and relevant local information can be found in the Investigator Site File (ISF).

A Coordinating Investigator will be responsible to coordinate Investigators at different centers participating in this multicenter trial. Tasks and responsibilities will be defined in a contract. Relevant documentation on the participating (Principal) Investigators and other important participants, including their curricula vitae, will be filed in the electronic trial master file.

Boehringer Ingelheim has appointed a Trial Clinical Monitor, responsible for coordinating all required activities, in order to

- manage the trial in accordance with applicable regulations and applicable Boehringer Ingelheim and CRO SOPs,
- direct the clinical trial team in the preparation, conduct, and reporting of the trial,
- ensure appropriate oversight of vendors.

A list of responsible persons and relevant local information can be found in the ISF.

A central laboratory service and an Interactive Response Technology (IRT) vendors will be used in this trial. Details will be provided in the IRT Manual and Central Laboratory Manual, available in the ISF.

3.2 DISCUSSION OF TRIAL DESIGN, INCLUDING THE CHOICE OF CONTROL GROUP

The current trial is being performed to establish an equivalence of efficacy between BI 695501 and US-licensed Humira in patients with active moderate to severe chronic plaque psoriasis.

This is a randomized, double-blind, parallel arm, multiple dose, active comparator trial of BI 695501 and US-licensed Humira with a planned 24-week treatment period followed by a 10-week safety follow up, in patients with active moderate to severe chronic plaque psoriasis.

The treatment groups will be blinded throughout the whole trial, to minimize any bias that could be introduced by knowledge of the treatment by either the investigator or the patient.

3.3 SELECTION OF TRIAL POPULATION

A total of approximately 300 patients is planned to be randomized in the current trial.

A log of all patients enrolled into the trial (i.e., who have signed informed consent) will be maintained in the ISF at the investigational site irrespective of whether they have been treated with investigational drug or not.

3.3.1 Main diagnosis for trial entry

Patients must have moderate to severe chronic plaque psoriasis, stable for the last 2 months with no meaningful changes in morphology or significant flares, defined as $\geq 10\%$ body surface area (BSA) involvement, Psoriasis Area and Severity Index (PASI) score ≥ 12 and static Physician's Global Assessment (sPGA) score ≥ 3 .

Please refer to Section 8.3.1 (Source Documents) for the documentation requirements pertaining to the inclusion and exclusion criteria.

3.3.2 Inclusion criteria

1. Males and females aged ≥ 18 to < 80 years who have a diagnosis of moderate to severe chronic plaque psoriasis (with or without psoriatic arthritis) for at least 6 months before the first administration of study drug (a self-reported diagnosis confirmed by the investigator is acceptable), and which has been stable for the last 2 months with no changes in morphology or significant flares at both Screening and Baseline (Randomization):
 - a. involved BSA $\geq 10\%$ and
 - b. PASI score ≥ 12 and
 - c. sPGA score of ≥ 3 .
2. Participants of reproductive potential (childbearing potential¹) must be willing and able to use highly effective methods of birth control per International Council for Harmonization (ICH) M3 (R2) that result in a low failure rate of less than 1% per year when used consistently and correctly during the trial and for 6 months following completion or discontinuation from the trial medication. A list of contraception methods meeting these criteria is provided in the [Section 4.2.2.2](#) and patient information.
3. Signed and dated written informed consent in accordance with Good Clinical Practice (GCP) and local legislation prior to admission to the trial.
4. Patients who are candidates for systemic therapy.

¹ Women of childbearing potential are defined as:

- having experienced menarche and
- not postmenopausal (12 months with no menses without an alternative medical cause) and
- not permanently sterilized (e.g., tubal occlusion, hysterectomy, bilateral oophorectomy or bilateral salpingectomy).

3.3.3 Exclusion criteria

1. Active ongoing inflammatory diseases other than psoriasis that might confound trial evaluations according to investigator's judgment.
2. Previous treatment with more than 1 biological agent, or adalimumab or adalimumab biosimilar. No prior biologic exposure within last 6 months of screening will be permitted
3. Patients with a significant disease other than psoriasis and/or a significant uncontrolled disease (such as, but not limited to, nervous system, renal, hepatic, endocrine, hematological, autoimmune or gastrointestinal disorders). A significant disease is defined as a disease which, in the opinion of the investigator, may (i) put the patient at risk because of participation in the trial, or (ii) influence the results of the trial, or (iii) cause concern regarding the patient's ability to participate in the trial.
4. Major surgery (major according to the investigator's assessment) performed within 12 weeks prior to randomization or planned within 6 months after screening, e.g., total hip replacement.
5. Any documented active or suspected malignancy or history of malignancy within 5 years prior to screening, except appropriately treated basal cell carcinoma of the skin or in situ carcinoma of uterine cervix.
6. Patients who must or wish to continue the intake of restricted medications (see Section 4.2.2.1) or any drug considered likely to interfere with the safe conduct of the trial.
7. Currently enrolled in another investigational device or drug study, or less than 30 days since ending another investigational device or drug study(s), or receiving other investigational treatment(s).
8. Chronic alcohol or drug abuse or any condition that, in the investigator's opinion, makes the patient an unreliable study subject or unlikely to complete the trial.
9. Women who are pregnant, nursing, or who plan to become pregnant during the course of this study or within the period at least 6 months following completion or discontinuation from the trial.
10. Forms of psoriasis (e.g., pustular, erythrodermic and guttate) other than chronic plaque psoriasis. Drug-induced psoriasis (i.e., new onset or current exacerbation from e.g., beta-blockers or lithium).
11. Primary or secondary immunodeficiency (history of, or currently active), including known history of HIV infection or a positive HIV test at screening (per the investigator discretion and where mandated by local authorities).
12. Known chronic or relevant acute tuberculosis,; IGRA TB test or PPD skin test will be performed according to the labelling for Humira. If the result is positive, patients may participate in the study if further work up (according to local practice/guidelines) establishes conclusively that the patient has no evidence of active tuberculosis. If latent tuberculosis is confirmed, then treatment must have been initiated before randomization and continued according to local country guidelines².

² For Germany: patients with positive IGRA TB test or PPD skin test will be excluded from the study participation.

13. Known clinically significant coronary artery disease, significant cardiac arrhythmias, moderate to severe congestive heart failure (New York Heart Association Classes III or IV) or interstitial lung disease observed on chest X-ray.
14. History of a severe allergic reaction, anaphylactic reaction, or hypersensitivity to a previously used biological drug or its excipients.
15. Positive serology for hepatitis B virus (HBV) or hepatitis C virus (HCV).
16. Receipt of a live/attenuated vaccine within 12 weeks prior to the Screening Visit; patients who are expecting to receive any live/attenuated virus or bacterial vaccinations during the trial or up to 3 months after the last dose of trial drug.
17. Any treatment (including biologic therapies) that, in the opinion of the investigator, may place the patient at unacceptable risk during the trial.
18. Known active infection of any kind (excluding fungal infections of nail beds), any major episode of infection requiring hospitalization or treatment with intravenous (i.v.) anti-infectives within 4 weeks of the Screening Visit or completion of oral anti-infectives within 2 weeks of the Screening Visit.
19. Aspartate aminotransferase (AST) or alanine aminotransferase (ALT) > 2.5 times upper limit of normal (ULN) at Screening.
20. Hemoglobin < 8.0 g/dL at Screening.
21. Platelets < 100,000/ μ L at Screening.
22. Leukocyte count < 4000/ μ L at Screening.
23. Creatinine clearance < 60 mL/min/1.73 m² at Screening.
24. Patients with a history of any clinically significant adverse reaction to murine or chimeric proteins, or natural rubber and latex, including serious allergic reactions.

3.3.4 Removal of patients from therapy or assessments

3.3.4.1 Removal of individual patients

All patients have the right to withdraw from the study at any time without the need to justify their decision. The investigator has the right to remove patients from the study for non-compliance or other reasons.

An individual patient is to be withdrawn from trial treatment if:

- The patient decides to discontinue participation in the trial by withdrawal of consent. In this case, no more investigations will be performed.
- The patient needs to take concomitant drugs that interfere with the investigational product or other trial medication.
- Lack of efficacy defined as PASI 50 not reached at Week 16.
- Development of a toxicity or adverse event which warrants BI 695501/Humira discontinuation including but not limited to serious adverse events (SAEs) or suspected unexpected serious adverse reactions (SUSARs).
- The patient has an AE that is categorized as a serious infection. A serious infection is defined as an infection requiring i.v. antibiotics or meeting the regulatory definition of a

SAE (including, but not limited to, systemic fungal infections, HIV, HBV, HCV, TB, infected joint prosthesis).

- The patient can no longer be treated with trial medication for other medical reasons (such as surgery, adverse events, other diseases, or pregnancy).
- If the trial treatment is not in the patient's best interest at the investigator's discretion. (e.g. severe worsening of psoriasis). The patient will be discontinued from the trial to receive treatment as deemed appropriate by the investigator.
- The patient has repeatedly shown to be non-compliant with important trial procedures and, in the opinion of both the investigator and sponsor representative, is not willing or able to adhere to the trial requirements in the future.

If a patient permanently discontinues trial medication for any reason (including lack of efficacy), every effort should be made to have the patient return for a safety follow-up visit 10 weeks after the last dose of trial medication.

Given the patient's agreement, the patient will undergo the procedures for early treatment discontinuation and follow-up as outlined in the [Flow Chart](#) (Safety Follow-up [SFU] visit) and Section 6.2.3.

For all patients the reason for withdrawal (e.g., AEs) must be recorded in the electronic Case Report Form (eCRF). These data will be included in the trial database and reported.

3.3.4.2 Discontinuation of the trial by the sponsor

Boehringer Ingelheim reserves the right to discontinue the trial overall or at a particular trial site at any time for reasons including but not restricted to:

1. Failure to meet expected enrolment goals overall or at a particular trial site
2. Emergence of any efficacy/safety information invalidating the earlier positive benefit-risk assessment that could significantly affect the continuation of the trial
3. Violation of GCP, the Clinical Trial Protocol (CTP), or the contract impairing the appropriate conduct of the trial.

The Investigator / the trial site will be reimbursed for reasonable expenses incurred in case of trial termination (except in case of the third reason).

4. TREATMENTS

4.1 INVESTIGATIONAL TREATMENTS

The trial medication will be provided by BI.

4.1.1 Identity of the Investigational Medicinal Products

BI 695501 and US-licensed Humira will be used in this study. Details of the trial medication are provided in Tables 4.1.1: 1, and [4.1.1: 2](#).

Table 4.1.1: 1 Test product

Substance:	BI 695501
Pharmaceutical formulation:	Solution for injection in prefilled syringe
Source:	BI Pharma GmbH & Co. KG, Germany
Unit strength:	40 mg / 0.8 mL
Posology	80 mg (loading dose) on Day 1 / Week 0, 40 mg every other week from Week 2 to Week 23
Route of administration:	Subcutaneous injection

Table 4.1.1: 2 Reference product

Substance:	US-licensed Humira (adalimumab)
Pharmaceutical formulation:	Solution for injection in prefilled syringe
Source:	AbbVie Inc.
Unit strength:	40 mg / 0.8 mL or 40 mg / 0.4 mL
Posology	80 mg (loading dose) on Day 1 / Week 0, 40 mg every other week from Week 1 to Week 23
Route of administration:	Subcutaneous injection

BI 695501 prefilled syringe will be provided as sterile, preservative-free, non-pyrogenic, single-use prefilled glass syringes containing 40 mg of BI 695501 per 0.8 mL. One syringe will be used per injection except for Week 0/Day 1, at which 2 syringes (80 mg) will be used. The needle cap of the syringe contains dry, natural rubber.

US-licensed Humira will be provided in sterile, preservative-free, non-pyrogenic, single-use, prefilled glass syringes containing 40 mg of adalimumab per 0.8 mL or 0.4 mL of solution. One syringe will be used per injection except for Week 0 / Day 1, at which 2 syringes (80 mg) will be used.

Any unused product or waste material will be disposed of in accordance with local requirements.

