Methodology:	
This is a randomized, double-blind, parallel-arm, multiple-dose, active comparator trial of BI 695501 and US-licensed Humira with a screening period of up to 28 days, a 24-week treatment period and a 10-week safety follow-up period in patients with chronic plaque psoriasis and a primary endpoint assessment at Week 16.
 
Patients will be randomized 1:1 to either BI 695501 or Humira. Each patient will receive 80 mg of BI 695501 or US-licensed Humira at Baseline (Randomization) (Day 1, Week 0), followed by 40 mg of BI 695501 or Humira 1 week later (Week 1), and then 40 mg of BI 695501 or Humira every other week. After Week 16, only patients who achieve a 50% reduction in Psoriasis Area and Severity Index (PASI 50) will continue the trial receiving their originally randomized treatment. Those patients not achieving at least PASI 50 will not be treated further with the study drugs but only followed up for safety.
		
No. of patients: Total entered:	Approximately 300 patients will be randomized.		
Each treatment:	Patients will be allocated to treatment in a 1:1 ratio to receive BI 695501 or US-licensed Humira.		
Diagnosis:	Moderate to severe chronic plaque psoriasis.		
Main criteria for inclusion:	
This study will include male or female participants at least 18 years of age who have a diagnosis of moderate to severe chronic plaque psoriasis of at least 6 months duration. The patient's chronic plaque psoriasis must have been stable for the last 2 months with no meaningful changes in morphology or significant flares. At inclusion, patients must have a PASI score ≥ 12, Static Physician's Global Assessment of psoriasis (sPGA) ≥ 3, and a body surface area (BSA) involvement $\geq 10\%$ at Screening and at baseline. Patients must be suitable for systemic treatment.
		

Name of company:		Boehringer Ingelheim	
Name of finished product:		NA	
Name of active ingredient:		BI 695501	
Protocol date: 26 Apr 2016	Trial number: 1297.12		Revision date:
	Patients with prior exposure to more than 1 biologic (must not be adalimumab) will be excluded from this trial.		
Test product(s):	BI 695501, solution for subcutaneous (s.c.) injection in single-use prefilled syringe (40 mg)		
dose:	Starting 1 week after a first administration of 80 mg BI 695501 after randomization, patients will receive 40 mg every other week.		
mode of administration:	Subcutaneous injection		

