Abbreviations: ; AE=adverse event; anti-HBc=anti-hepatitis B core antibodies; anti-HCV=anti-hepatitis C antibodies; DLQI=Dermatology Life Quality Index; EoT=End of Treatment; IRT=Interactive Response Technology; HBsAg=hepatitis B surface antigen; HIV=human immunodeficiency virus; IGRA=interferon gamma-releasing assay; ; PASI=Psoriasis Area and Severity Index; PPD=purified protein derivative; SFU=Safety Follow-up; sPGA=Static Physician's Global Assessment of psoriasis; TB=tuberculosis.

1. Patients will have to visit the site for efficacy assessments and to provide samples for / safety. For other visits (Weeks 3, 5, 7, 9, 11, 13, 15, 17, 19, 21 and 23), patients are allowed to self-administer the drug at home (after training).
2. Patients who discontinue the trial early (also those not achieved PACI 50 at week 16) will, at discontinuation, have an End of Treatment (EoT) Visit equivalent to the Week 24 assessments (except trial medication administration). Every effort should be made for all patients to return for a Safety Follow-up (SFU) Visit 10 weeks after last drug administration.
3. All efficacy (e.g., PASI, and sPGA) and safety assessments will be performed by blinded personnel.
4. A chest X-ray is to be taken at Screening. Alternatively, results from a chest X-ray taken within 12 weeks of Screening can be used.
5. Patients must have a negative tuberculosis (TB) screening assessment, including a purified protein derivative (PPD) skin test or interferon gamma-releasing assay (IGRA) (e.g., QuantiFERON[®] TB Gold or T-SPOT[®].TB). In addition, a TB test can be performed at any time during the trial if the investigator considers it clinically necessary.
6. Vital signs include measurement of body temperature, blood pressure, and pulse rate (all in the sitting position after a 5-minute rest).
7. Adverse events (AEs) will be collected from the time of informed consent. Adverse events continuing at the SFU Visit must be followed to resolution or followed up as agreed by the investigator and medical monitor. For patients who complete the trial or who discontinue the trial early, new AEs will be captured for up to 10 weeks after last drug administration (SFU Visit).
- 8.
9. Trial medication should be administered at Day 1, with the second injection 7 days later and subsequent injections every 2 weeks thereafter (\pm 2 days up to Week 14 and \pm 3 days from Week 16 onward).

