4.1.2 Selection of doses in the trial

In the US and EU, adalimumab (Humira) has received health authority approval for the treatment of RA, Crohn's disease, plaque psoriasis, psoriatic arthritis, ankylosing spondylitis, juvenile idiopathic arthritis and Hidradenitis suppurativa. The doses of BI 695501 and Humira selected for this trial are identical due to the similarity of both compounds (an initial dose of 80 mg s.c. injection followed 1 week later and subsequently every other week by 40 mg) and are the doses that were used to assess the efficacy of the originator compound and are as per Humira label.

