4.1.4 Drug assignment and administration of doses for each patient

Each patient will receive 80 mg of BI 695501 or US-licensed Humira at the Baseline Visit (Day 1, Week 0) followed by 40 mg of BI 695501 or US-licensed Humira 1 week later, and then 40 mg of BI 695501 or US-licensed Humira every other week until Week 16 (primary endpoint).

After Week 16 (Day 112), patients achieving at least a PASI 50 response will continue receiving their randomized treatment (40 mg BI 695501 or Humira every other week) until Week 24 in a blinded fashion.

Patients not achieving at least PASI 50 at Week 16 will not be further treated with the study drugs, but only followed up for safety.

The prefilled syringe must be removed from refrigeration 30 minutes before administration to permit the medication to warm. Injecting cold medication can cause discomfort. Once taken out of the refrigerator, the trial medication should be administered within 1 hour. A syringe must not be used if it is frozen or if it has been left in direct sunlight.

The patient will administer the injection in an area of the skin where post-administration assessments of any reaction would not be compromised by the presence of impairment to skin integrity. The location for the trial medication injection will be the lower abdomen (excluding a 2-inch [5-cm] area around the navel) and upper thigh. A different injection site should be selected for each injection (at least 1 inch [2.5 cm] away from the previous site).

For the duration of the trial, trial medication will be administered either at the trial site by dedicated trial personnel, or at home by the patients themselves. At all designated site visits (Weeks 0 and 1), the patient must administer BI 695501 while at the trial site. Between designated site visits (Weeks 3, 5, 7, 9, 11, 13, 15, 17, 19, 21, and 23), the patient may choose to come to the site to self-inject the trial medication with the support of suitably qualified, designated trial site personnel or the patient may self-inject the trial medication at home. Patients will be instructed to accurately record the dates and times of dosing, problems encountered with dosing, the occurrence of any AEs, the use of concomitant therapies, and the prefilled syringe storage conditions on the provided diary cards between the trial site visits.

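### The two product tables in Protocol 4.1.1 start the 40 mg every-other-week dosing in different weeks for the two arms, against the single schedule stated everywhere else

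*Protocol*

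**What the plan says.** Protocol 4.1.1 has one table per product. Both give an 80 mg loading dose on Day 1. For BI 695501, Table 4.1.1: 1 then has "40 mg every other week from Week 2 to Week 23". For Humira, Table 4.1.1: 2 has "40 mg every other week from Week 1 to Week 23".

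The other schedule statements make no distinction between the arms:

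- Section 4.1.2: "The doses of BI 695501 and Humira selected for this trial are identical due to the similarity of both compounds", and the regimen is "an initial dose of 80 mg s.c. injection followed 1 week later and subsequently every other week by 40 mg".
- Synopsis, test product: "Starting 1 week after a first administration of 80 mg BI 695501 after randomization, patients will receive 40 mg every other week". The comparator entry has the same timing.
- Flow Chart footnote 9: "Trial medication should be administered at Day 1, with the second injection 7 days later and subsequent injections every 2 weeks thereafter".
- Section 4.1.4: the 80 mg dose is "followed by 40 mg of BI 695501 or US-licensed Humira 1 week later". Later doses are on odd weeks from 3 to 23, and the last planned injection is at Week 23 with no extension beyond it.
- SAP section 13 lists administration on Day 1, on Day 8 and then every other week to Day 162. SAP section 14.1 has one planned-usage table for both arms, reaching 14 injections at Visit 9.

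**The concern.** An equivalence comparison of two versions of the same drug needs the same regimen in both arms. Here the section that defines the trial products gives one arm a different start week, and nothing in the documents explains it.

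If the entry were followed, BI 695501 patients would have their second administration one week later than Humira patients. They would then stay on even weeks while the other arm stayed on odd weeks. The arms would differ in dosing history before the Week 16 PASI 75 assessment, and the dosing week would itself identify the treatment.

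The most plausible route is the third-party blinding procedure. Under it, unblinded staff give the injections, and Appendix 10.3 refers to Table 4.1.1: 1 for the description of the trial medication, without citing Table 4.1.1: 2.

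**Working it through.** **Inputs.** Start weeks come from Tables 4.1.1: 1 and 4.1.1: 2. The Week 23 end comes from both tables and Section 4.1.4. Two syringes at Week 0 and one at each later dose come from Section 4.1.1. Visits 2 to 9 fall at Weeks 0, 1, 4, 8, 12, 16, 20 and 24 (Flow Chart). Planned usage comes from SAP section 14.1.

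**Formula.** Total injections = 2 + number of weeks in {start, start + 2, ...} not later than Week 23. Each injection is counted at the first visit on or after its dosing week.

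**Reproducing the SAP figure.** A Week 1 start gives Weeks 1, 3, ..., 23, which is 12 doses, and 2 + 12 = 14. This matches the SAP table at every visit.

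**Literal Table 4.1.1: 1.** A Week 2 start gives Weeks 2, 4, ..., 22, which is 11 doses, and 2 + 11 = 13. Week 23 is not in the series, so the entry's start, interval and end cannot all hold.

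| | Week 1 start | Week 2 start | SAP 14.1 |
|---|---|---|---|
| Visit 2 | 2 | 2 | 2 |
| Visit 3 | 1 | 0 | 1 |
| Visit 4 | 1 | 2 | 1 |
| Visits 5 to 8, each | 2 | 2 | 2 |
| Visit 9 | 2 | 1 | 2 |
| Total injections | 14 | 13 | 14 |
| Total dose | 80 + 12 × 40 = 560 mg | 80 + 11 × 40 = 520 mg | not stated |

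**Up to Week 16.** The Week 1 series has 8 maintenance doses (Weeks 1 to 15), so 2 + 8 = 10 syringes, or 400 mg. The Week 2 series also reaches 10 syringes and 400 mg, but only if the Week 16 dose is counted. Section 6.1 puts assessments before dosing. On that basis, 2 + 7 = 9 syringes, or 80 + 7 × 40 = 360 mg, would precede the Week 16 PASI.

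**Would the planned checks show it?** SAP section 5.4 sends compliance outside 80% to 120% for medical review. A literal Week 2 start gives 13/14 = 92.9% overall, and 9/10 = 90% or 10/10 = 100% to Week 16. None of these triggers review. The descriptive outputs would show it: per-visit compliance would be 0/1 = 0% at Visit 3 and 2/1 = 200% at Visit 4, and the by-arm proportion treated on Day 8 (SAP section 13) would differ.

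**The case against.** The case on the other side is that this is probably a slip in one table cell and could hardly be acted on.

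- The Flow Chart has no Week 2 visit or dosing column.
- Section 4.1.4 requires a dose on site at Week 1 and Section 4.3 has it observed. Section 6.2.2 has an IRT contact and an administration at Visit 3.
- Home dosing and diary entries are on odd weeks for every patient.
- The IRT assigns a medication number for each administration. Staff who do not know the arm cannot apply one table to one arm. Even under third-party blinding, blinded staff make the IRT contacts.
- Section 4.1.4 governs administration. Section 4.1.1 describes the products, and Appendix 10.3 cites its table only as a description.
- The SAP uses one planned-usage table for both arms, so the compliance figures do not depend on the disputed entry.
- SAP version 2.0 is dated January 2018, and section 15.1.2.2 already draws on about 90% of subject data to Week 16. A late amendment would change little in practice.

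All of this stands as a limit on the consequence. It does not remove the contradiction: the tables give a dosing rule for one arm that conflicts with the rest of the plan and with its own end week.

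A reader might infer that the sponsor chose an arm-specific schedule. The documents do not support that, because Section 4.1.2 states that the doses are the same. A reader might also infer that the Week 16 comparison is biased or the blind broken. That would follow only if a site followed the one entry against the visit schedule and the IRT, and nothing in the documents shows that this happened. Finally, a reader might run the Week 2 series on to Week 24 and count 12 doses. The entry's own Week 23 end and the Section 4.1.4 limit on the last injection both rule that out.

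**Conclusion.** The inconsistency is real and limited in size. Read literally, the tables separate the arms by one week at the second administration and by one injection (40 mg) over the trial: 13 injections and 520 mg against 14 and 560 mg. The Week 2 entry is also impossible as written.

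The counts assume no missed or shifted doses and a patient who continues treatment after Week 16. Any effect on the Week 16 comparison or on blinding is conditional on the entry being followed, which the plan's own procedures make unlikely. Sample size, power, alpha and the planned analysis are unaffected. It should be corrected because it is a dosing statement for one arm of a blinded equivalence trial, and the overall compliance screen would not flag a departure of this kind.

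**What to change.** Reconcile Tables 4.1.1: 1 and 4.1.1: 2 with each other and with the synopsis, Flow Chart, Sections 4.1.2 and 4.1.4 and the SAP planned-usage table, so that one schedule appears throughout. The sponsor determines which entry is correct. Appendix 10.3 should refer to both product tables.

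The cost is a text change in a protocol amendment or, if conduct is too far advanced, a documented clarification. No new data or analyses are needed. The by-arm, by-visit exposure output already planned in SAP section 13 can be used to confirm that the two arms were dosed in the same weeks.
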